4.1.3 Administration of Study Intervention

All participants will be treated starting on Day 1 through Week 92 according to their respective treatment group. The IRT will determine the dosing schedule and adjust it in consideration of missed visits, out of window visits, and missing data during a visit. If a visit is missed at which study treatment is scheduled to be administered, the missed dose should be made up as close to the originally scheduled visit as possible using an unscheduled visit. Adjustments to study intervention due to development of sight-threatening complications of DR are described in Section 4.1.3.1.

As shown in the dosing regimen schematic provided in Figure 1, participants will be treated according to the group to which they were randomized, as follows:

• Group A - KSI-301 5 mg via Intravitreal Injection:

Intravitreal KSI-301 5 mg injection will be administered on Day 1, Week 8, Week 20, Week 44, Week 68, and Week 92.

• Group B - Sham Injection:

To preserve study masking, sham injections are administered to Group B participants at visits in which KSI-301 is administered to Group A participants. Thus, sham injections will be administered on Day 1, Week 8, Week 20, Week 44, Week 68, and Week 92.

For all study participants, non-treatment study visits will occur on Week 32, Week 48, Week 56, Week 80, and Week 96. A final safety assessment will occur on Week 100 and will be done via telephone call for all participants, except in WOCBP, in which case a site visit is required to administer a pregnancy test.

		Year 1								PE				
Week		0	(4)	8	(12)	(16)	20	(24)	(28)	32	(36)	(40)	44	48
KSI-301 5 mg	Q24W													
Sham		0		0			0						0	
						Ĩ	Year 2						SE	SA
Week		(52)	56	(60)	(64)	68	(72)	(76)	80	(84)	(88)	92	96	100 ª
KSI-301 5 mg	Q24W													
Sham						0						0		

Figure 1: Protocol KS301P106: Masked Dosing Regimens by Week

Abbreviations: PE = primary endpoint; Q24W = once every 24 weeks; SA = safety assessment; SE = secondary endpoint.

^a Week 100 is a final safety assessment that will be done via telephone call for all participants, except in WOCBP, in which case a site visit is required for the safety assessment that includes a pregnancy test.

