9.4.3 Secondary Endpoint(s)

Key secondary endpoints will be assessed at Week 48, Week 96 and, if applicable, over time:

- Proportion of eyes developing any of the following from baseline:
 - PDR or ASNV;
 - Vitreous hemorrhage or tractional retinal detachment believe to be due to PDR; or
 - DME.
- Proportion of eyes developing PDR or ASNV from baseline.
- Proportion of eyes developing vitreous hemorrhage or tractional retinal detachment, believed to be due to PDR, from baseline.
- Proportion of eyes developing DME from baseline.
- Proportion of eyes with a \geq 2-step improvement from baseline on DRSS from baseline.
- Proportion of eyes with a \geq 2-step worsening from baseline on DRSS from baseline.
- Proportion of eyes with a \geq 3-step improvement from baseline on DRSS from baseline.
- Proportion of eyes with a \geq 3-step worsening from baseline on DRSS from baseline.
- Time to first development of either PDR, ASNV, or DME.
- Time to first development of PDR or ASNV.
- Time to first development of vitreous hemorrhage or tractional retinal detachment, believed to be due to PDR.
- Time to first development of DME.
- Time to first development of a \geq 2-step improvement on the DRSS.
- Time to first development of a \geq 2-step worsening on the DRSS.
- Time to first development of a \geq 3-step improvement on the DRSS.
- Time to first development of a \geq 3-step worsening on the DRSS.
- Mean change in SD-OCT central subfield thickness (CST) from baseline.

CONFIDENTIAL

- Mean change in BCVA from baseline.
- Proportion of eyes who lose ≥ 5 , ≥ 10 , or ≥ 15 letters in BCVA from baseline.
- Proportion of eyes with a BCVA score of ≥ 69 letters (20/40 approximate Snellen equivalent).
- Proportion of eyes with prolonged vision loss.
- Incidence of ocular and systemic adverse events up to Week 48 and Week 100.
- Systemic anti-drug antibody status over time (in the ADA-evaluable population).
- Systemic pharmacokinetic profile (i.e. systemic exposure) over time (in the PK-evaluable population).

Unless stated otherwise, all analyses described will be performed on the ITT population.

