2.0 STUDY OBJECTIVES AND ENDPOINTS

Table 1 lists the primary, key secondary and additional secondary study objectives, along with their corresponding endpoints.

Table 1: Objectives and Endpoints

Table 1: Objectives and Endpoints Objectives	Corresponding Endpoints
	Corresponding Endpoints
Primary To demonstrate that KSI-301 5 mg is superior to sham treatment, with respect to proportion of eyes improving ≥2 steps on Diabetic Retinopathy Severity Scale (DRSS) from baseline at Week 48.	• The proportion of eyes improving ≥2 steps on DRSS from baseline at Week 48.
Key Secondary	
To demonstrate that KSI-301 5 mg is superior to sham treatment, with respect to proportion of eyes with vision-threatening complications of diabetes, and proportion of eyes improving \geq 3 steps on Diabetic Retinopathy Severity Scale (DRSS).	 Proportion of eyes developing any of the following from baseline through Week 48: PDR or ASNV; Vitreous hemorrhage or tractional retinal detachment believed to be due to PDR; or DME.
	• Proportion of eyes improving ≥3 steps on DRSS from baseline at Week 48.
	• Proportion of eyes developing PDR through Week 48.
Additional Secondary	
To evaluate the efficacy of KSI-301 5 mg compared to sham treatment.	• Proportion of eyes developing PDR or ASNV from baseline through Week 48.
	• Proportion of eyes developing vitreous hemorrhage or tractional retinal detachment, believed to be due to PDR, from baseline through Week 48.
	• Proportion of eyes developing DME from baseline through Week 48.
	• Proportion of eyes with a ≥2-step worsening from baseline on DRSS from baseline at Week 48.
	• Proportion of eyes with a ≥3-step worsening from baseline on DRSS from baseline at Week 48.
	• Time to first development of PDR, ASNV, or DME through Week 48.
	• Time to first development of PDR or ASNV through Week 48.
	• Time to first development of vitreous hemorrhage or tractional retinal detachment, believed to be due to PDR through Week 48.
	• Time to first development of DME through Week 48.
	• Mean change in SD-OCT central subfield thickness (CST) from baseline by visit over time.
	• Mean change in BCVA from baseline by visit over time.
	• Proportion of eyes who lose ≥ 5 , ≥ 10 , or ≥ 15 letters in BCVA from baseline by visit over time.

KS301P106 SAP Version 1.0 KSI-301 – Kodiak Sciences Inc.

Objectives	Corresponding Endpoints
To evaluate the safety and tolerability of KSI-301	Incidence of ocular and systemic adverse events up to Week 48.

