8.0 SAFETY EVALUATION

Safety analyses will be performed for the Safety Analysis Set. In the Primary Analysis, safety data from Day 1 to Week 48 will be summarized by treatment group.

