8.1 Exposure to Study Medication

Study eye exposure to study medication will be summarized (open-label KSI-301 5mg treatment will not be included here). Summaries will include:

- Mean (SD) and median number of injections, and number of patients receiving ≥1 injection, 1, 2, 3, 4, 5, etc. of KSI-301 or sham injections from Day 1 to Week 48 and from Day 1 to the end of study.
- Duration of study drug exposure (mean [SD] and median, in months) for subjects receiving KSI-301 5 mg or sham.
- Listings will include treatment (KSI-301, sham) and date of injection.

For patients who develop sight-threatening complication(s), exposure to open-label KSI-301 5mg treatment will be summarized and listed similarly as above.

A listing of patients who received study treatment other than the one assigned at randomization will include the randomized treatment, the actual administered treatment, Visit, and study Day. A separate listing will list patients who receive open-label KSI-301 5mg treatment with the same variables.

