8.2 Adverse Events

Adverse events (AEs) will be coded to a MedDRA version 23.1 or later. AEs and Serious AEs (SAEs) will be summarized and listed by ocular events for the treated eye (or study eye), ocular events for the non-treated eye (or fellow eye), and non-ocular (systemic) events.

Treatment emergent AEs (TEAEs) are events with onset date on or after the initiation of study treatment through the last dose date of study treatment + 28 days, start date of non-study anti-

VEGF in study eye on or after last dose date, or start date of open-label KSI-301 treatment due to development of sight-threatening complication, whichever occurs first.

If the severity score of an adverse event is missing, the severity score will be imputed as severe. If the relatedness of an adverse event is missing, the adverse event will be considered related.

At each level of summarization (e.g., any AE, system organ class, and preferred term), subjects experiencing more than one TEAE will be counted only once. In the summary of TEAEs by severity grade, subjects will be counted once at the highest severity reported at each level of summarization.

Frequency tables including patients' incidence rates will be provided through Week 48 for the following:

- Ocular TEAEs and treatment-emergent serious AEs (TESAEs) (study eye and fellow eye separately)
- Non-ocular TEAEs and TESAEs
- Ocular TEAEs leading to study treatment discontinuation (study eye and fellow eye separately)
- Ocular TEAEs by severity (study eye and fellow eye separately)
- Non-ocular TEAEs by severity
- Related ocular TEAEs (study eye and fellow eye separately) by severity
- Related non-ocular TEAEs by severity
- Intraocular inflammation TEAEs and TESAEs not associated with infection, autoimmunity, drug toxicity, or traumatic etiologies (study and fellow eye separately).
- IOI TEAEs and TESAEs associated with infection (study and fellow eye separately).
- IOI TEAEs and TESAEs associated with autoimmune, drug toxicity, or trauma (study and fellow eye separately).
- Arteriothromboembolic (ATE) Adverse Events. ATEs will be tabulated as those events meeting the Anti-Platelet Trialists' Collaboration criteria (i.e., nonfatal

myocardial infarction, nonfatal stroke, and vascular death, including deaths of unknown cause)

- Adverse events of special interest [AESI] (study eye, fellow eye and non-ocular combined), as defined in the protocol Section 8.3.6
- Injection procedure related TEAEs and TESAEs in study eye

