- Non-serious TEAEs and TESAEs (study eye, fellow eye and non-ocular combined)

All AEs and serious AEs will be presented separately in data listings by treatment group, subject ID, and event date. Adverse events from patients who remain in the study after study treatment discontinuation will be listed.

For subjects who receive open-label KSI-301 5mg treatment due to development of sightthreatening complications, ocular TEAEs and TESAEs for study eye starting from when subjects switch to open-label KSI-301 treatment will be summarized until the end of study. All AEs (study eye, fellow eye and non-ocular) will be presented in a data listing by subject ID, and event date.

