10.0 SUMMARY OF CHANGES IN THE CONDUCT OF THE STUDY OR PLANNED ANALYSES

The Week 100 analyses will not be performed per protocol, since the study was discontinued early by the Sponsor.

In this SAP, the Sponsor has defined the primary estimand, analysis populations, and strategies for addressing intercurrent events, missing data, and a set of sensitivity analyses for the primary efficacy outcome. Where relevant, these definitions take precedence over those defined in the study protocol.

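### By-arm adverse-event tables stop at Week 48, so later treatment-emergent events on masked treatment are listed but not tabulated, and the SAP does not say why other outputs run to end of study

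*SAP*

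**What the plan says.** Protocol 9.4.3 lists the safety endpoint as "Incidence of ocular and systemic adverse events up to Week 48 and Week 100". Protocol 8.3.1 collects adverse events from Day 1 to Week 100 or early termination. The masked schedule is in Protocol 4.1.3: "Intravitreal KSI-301 5 mg injection will be administered on Day 1, Week 8, Week 20, Week 44, Week 68, and Week 92". Sham follows the same visits.

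The SAP narrows the endpoint. Its Table 1 (Section 2.0) has "Incidence of ocular and systemic adverse events up to Week 48", with no Week 100 counterpart. Section 8.0 says that in the primary analysis "safety data from Day 1 to Week 48 will be summarized by treatment group". Section 8.2 says that "incidence rates will be provided through Week 48 for the following", and its list covers all the adverse-event frequency tables by arm. Section 3.1 reports that the sponsor decided in late July 2023 to stop development and that data after Week 48 will be incomplete. Section 10.0 adds: "The Week 100 analyses will not be performed per protocol, since the study was discontinued early by the Sponsor".

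Other outputs in the same SAP go further. Section 8.1 counts injections "of KSI-301 or sham injections from Day 1 to Week 48 and from Day 1 to the end of study". Section 6.1 tabulates discontinuations by Week 48 and by end of study. Table 4 runs the repeated-measures analyses of central subfield thickness (CST) and BCVA to both points. For participants who move to open-label treatment, Section 8.2 says that study-eye ocular events "starting from when subjects switch to open-label KSI-301 treatment will be summarized until the end of study".

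**The concern.** The treatment-emergent definition in SAP 8.2 runs to 28 days after the last dose, unless open-label KSI-301 or a non-study anti-VEGF drug in the study eye starts first. An event after a masked Week 68 or Week 92 dose can therefore be treatment-emergent by the SAP's own definition and still enter no incidence table. With the Week 100 analyses cancelled, no later analysis picks it up.

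This matters because the masked arms are the only concurrent safety comparison against sham. Protocol Table 2 names intraocular inflammation and arterial thromboembolic events as potential risks, and repeated dosing in the second year is where a late signal could show. A listing gives the events but no cumulative incidence, denominator or person-time by arm.

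Incomplete follow-up does not by itself explain the cut-off, because the SAP treats the same incomplete period as usable for exposure, discontinuations, CST, BCVA and open-label study-eye events.

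**Working it through.** The plan states no figure of its own on this point. The check sets the reporting periods side by side and then counts doses and weeks.

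**1. Reporting period by output**

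| Output | Source | Period |
|---|---|---|
| By-arm adverse-event frequency tables | SAP 8.2 | Week 48 |
| Masked injections | SAP 8.1 | Week 48 and end of study |
| Discontinuations | SAP 6.1 | Week 48 and end of study |
| CST and BCVA | SAP Table 4 | Week 48 and end of study |
| Study-eye ocular events after open-label switch | SAP 8.2 | End of study |
| Listings of adverse events, serious events, deaths | SAP 8.2, 8.3 | No Week 48 limit stated |
| Fellow-eye and non-ocular events after open-label switch | SAP 8.2 | Listing only |

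**2. Planned masked injections (Protocol 4.1.3)**

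- By Week 48: Day 1, Weeks 8, 20 and 44, which is 4.
- After Week 48: Weeks 68 and 92, which is 2.
- Share outside the tables: 2/6 = 33%.

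**3. Treatment-emergent window at nominal visit times (last dose + 4 weeks)**

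- Last masked dose at Week 44: 44 + 4 = Week 48, so nothing is cut off.
- Last masked dose at Week 68: 68 + 4 = Week 72, so 72 − 48 = 24 weeks are cut off.
- Last masked dose at Week 92: 92 + 4 = Week 96, so 96 − 48 = 48 weeks are cut off.

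Adverse-event collection runs to Week 100, that is, 100 − 48 = 52 weeks past the cut-off. The last 4 of these weeks are outside the treatment-emergent window whatever the table cut-off.

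**4. Ceiling on affected KSI-301 injections (120 planned per arm, Protocol 9.2)**

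- All scheduled: 120 × 6 = 720.
- By Week 48: 120 × 4 = 480.
- After Week 48: 720 − 480 = 240.

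The documents give no per-injection event rate. For an assumed range of 0.1% to 2%, the expected events outside the tables at the ceiling are 240 × 0.001 = 0.24 to 240 × 0.02 = 4.8. If half the later injections were given, the range is 0.12 to 2.4.

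**5. Could the later doses have been reached?**

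Take 31 July 2023 as the stop date (assumed from late July). Counting back 68 weeks gives 11 April 2022, and counting back 92 weeks gives 25 October 2021. Participants randomized by those dates could have reached Week 68 and Week 92 before the stop. The protocol is dated 17 May 2021, 115 weeks before the assumed stop date, so this was possible. The documents give no enrolment dates, so the number remains unknown.

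**The case against.** The strongest reply is that this is a disclosed choice of reporting format. SAP 3.1 and 10.0 state the early stop and the cancellation, and SAP Table 1 aligns the safety endpoint with Week 48. The events are reported: SAP 8.2 lists all adverse events by treatment group, subject and date, and SAP 8.3 lists deaths, serious and other significant events. If only a handful are affected, a reader can count them. Some later safety information is also summarized: discontinuation reasons, and intraocular pressure and vital signs by visit with no Week 48 limit stated (SAP 8.5, 8.7). No efficacy test is touched. All of this stands, and it limits the severity.

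A reader might infer four stronger things that the documents do not support:

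- *That late events are lost or the change is hidden.* They are listed by arm, and the cancellation is declared with its reason.
- *That the exposure table covers more injections than the adverse-event tables can be matched to.* SAP 8.1 also gives exposure to Week 48, which is the matching denominator.
- *That 52 of 100 weeks are missing from the tables.* That is the collection period. Treatment-emergent tables could recover at most 48 weeks.
- *That masked dosing is known to have continued to Weeks 68 and 92.* The protocol gives a schedule and the SAP provides for end-of-study exposure; neither says how many doses were given.

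The reply does not answer why incompleteness stops adverse events at Week 48 but not the other outputs. Protocol 9.4.1 already set the second-period analysis for when everyone had either completed Week 100 or discontinued, so truncated follow-up was provided for.

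**Conclusion.** The point holds as a reporting gap that should be closed. Followed as written, the SAP gives no by-arm incidence or denominator for treatment-emergent events after Week 48 in participants on masked treatment. This departs from the protocol's safety endpoint. Fellow-eye and non-ocular events after Week 48 in open-label switchers are likewise only listed; their study-eye events are summarized to end of study.

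On the planned schedule, the gap is 2 of 6 masked injections and up to 48 weeks of the treatment-emergent window, with a ceiling of 240 KSI-301 injections. The ceiling assumes 120 participants in the arm, all kept on masked treatment through Week 92. Early stopping and switches to open-label treatment both lower it, possibly by a lot. The event counts above rest on assumed rates and only illustrate scale. Confidence is high for the gap in the text and low for its size. The primary and key secondary efficacy analyses are unaffected.

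**What to change.** In SAP 8.2, beside the Week 48 tables, add by-arm tables from Day 1 to end of study for treatment-emergent and serious treatment-emergent events, intraocular inflammation, arterial thromboembolic events and events of special interest. Show person-time at risk, ending where the treatment-emergent window ends, or per-injection rates, which Protocol 9.4.5 already foresees for certain events. In SAP 10.0, limit the cancellation to the Week 96/100 efficacy analyses. In SAP Table 1, add the end-of-study safety endpoint.

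The treatment-emergent window closes when open-label treatment starts, so these tables will not pick up later fellow-eye and non-ocular events in switchers. Either state that these are listed only, or add them to the existing open-label summary.

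The cost is some SAP wording and one more run of existing table programs, with no new data and no effect on any hypothesis test. The downside is that follow-up after Week 48 is unequal and incomplete, so crude percentages must be read with the person-time.

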Intraocular inflammation	Intraocular inflammation has been reported following treatment with intravitreal anti-VEGF medicines, including KSI-301. Additional details are provided in IB Section 5.4.2.3.	Participants will be monitored following the injection and instructed to report any symptoms suggestive of intraocular inflammation without delay to facilitate early diagnosis and treatment (Section 8.1.4). Participants with active ocular infection or inflammation in either eye (e.g., blepharitis, infectious conjunctivitis, keratitis, scleritis, endophthalmitis) are excluded from this study (Section 5.2.1). Participants with active intraocular inflammation will have study treatment interrupted (Section 7.1.1)						
Hypersensitivity	Hypersensitivity reactions may manifest as rash, pruritus, urticaria, severe anaphylactic/ anaphylactoid reactions, or severe intraocular inflammation. Additional details are provided in IB Section 5.4.2.4.	Participants with known hypersensitivity to intravitreal agents such as aflibercept or ranibizumab or any ingredient of KSI-301 are excluded from this study (Section 5.2.2).						

Table 2:Protocol KS301P106: Risk Assessment

Study Procedures	5	
Risks associated with the method of administration	These risks include endophthalmitis, increases in intraocular pressure, retinal detachment, retinal tear, traumatic cataract, and intraocular hemorrhage. Additional details are provided in IB Section 5.4.2.5.	Proper and aseptic injection technique when administering intravitreal injections will be used (Section 8.1.3). Participants will be monitored following the injection and instructed to report any symptoms suggestive of endophthalmitis or retinal detachment without delay to facilitate early diagnosis and treatment (Section 8.1.4). Intraocular pressure and the perfusion of the optic nerve head will also be monitored and managed (Section 8.1.4). Participants with active ocular infection or inflammation in either eye (e.g., blepharitis, infectious conjunctivitis, keratitis, scleritis, endophthalmitis) are excluded from this study (Section 5.2.1).
Exposure to SARS-CoV-2 virus	Section 2.3.2.1	Section 2.3.2.1

 Table 2:
 Protocol KS301P106: Risk Assessment (Cont'd)

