There may be situations in which an SAE has occurred, and the Investigator has minimal information to include in the initial report to the Sponsor. However, it is very important that the Investigator always make an assessment of causality for every event before the initial transmission of the SAE data to the Sponsor.

The Investigator may change his/her opinion of causality in light of follow-up information and send an SAE follow-up report with the updated causality assessment.

The causality assessment is one of the criteria used when determining regulatory reporting requirements.

The relationship to the intravitreal injection procedure or to study intervention will be assessed using the following definitions:

- Not Related There is not a reasonable possibility that the AE is related to the injection procedure or to the study intervention.
- Related There is a reasonable possibility that the AE is related to the injection procedure or to the study intervention.

Follow-up of AEs and SAEs

- The Investigator is obligated to perform or arrange for the conduct of supplemental measurements and/or evaluations as medically indicated or as requested by the Sponsor to elucidate the nature and/or causality of the AE or SAE as fully as possible. This may include additional laboratory tests or investigations, histopathological examinations, or consultation with other health care professionals.
- If a participant dies during participation in the study or during a recognized follow-up period, the Investigator will provide the Sponsor with a copy of any post-mortem findings including histopathology if applicable.
- New or updated information will be recorded in the originally submitted documents.
- The Investigator will submit any updated SAE data to the Sponsor within 24 hours of receipt of the information.

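### SAP 8.2 splits intraocular inflammation into three tables by cause and plans no any-cause incidence by arm, so the number of participants with any inflammation cannot be read from the planned tables

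*SAP*

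**What the plan says.** SAP 8.2 (Adverse Events) lists the frequency tables to be produced through Week 48. Three concern IOI:

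- The first leaves out four kinds of cause: "Intraocular inflammation TEAEs and TESAEs not associated with infection, autoimmunity, drug toxicity, or traumatic etiologies (study and fellow eye separately".
- The second is confined to infectious cases: "IOI TEAEs and TESAEs associated with infection (study and fellow eye separately".
- The third pools the remaining three kinds of cause: "IOI TEAEs and TESAEs associated with autoimmune, drug toxicity, or trauma (study and fellow eye separately".

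They stand side by side, and the SAP ranks none above the others. Neither SAP 8.2 and 8.3 nor protocol 9.4.5 lists a table of IOI regardless of cause.

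The same SAP list also has "Ocular TEAEs and treatment-emergent serious AEs (TESAEs) (study eye and fellow eye separately", a version by severity, "Related ocular TEAEs (study eye and fellow eye separately) by severity", a table of injection-procedure-related events in the study eye, and a table of adverse events of special interest (AESI). The counting rule is: "At each level of summarization (e.g., any AE, system organ class, and preferred term), subjects experiencing more than one TEAE will be counted only once".

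Protocol Table 2 (section 2.3.2) states the risk: "Intraocular inflammation has been reported following treatment with intravitreal anti-VEGF medicines, including KSI-301". Section 10.3.3 has sites report ocular inflammation under separate terms (iritis, iridocyclitis, vitritis, endophthalmitis) and grade causality only as related or not related. Related means: "There is a reasonable possibility that the AE is related to the injection procedure or to the study intervention". Neither document defines drug toxicity, says whether it covers KSI-301, or says who assigns the cause of an IOI event and when.

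**The concern.** For an intravitreal anti-VEGF product with a named IOI risk, a reader of the safety report will first want to know how many participants in each arm had any IOI in the study eye. The planned tables answer that only in parts, and the parts need not add up to participants.

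The split may also act unevenly between the arms. Protocol Table 4 describes the sham as an empty syringe without a needle pressed on the eye. While participants receive masked treatment as assigned, study-eye inflammation caused by KSI-301 can therefore arise only in the KSI-301 arm. If such cases are classed as drug toxicity, they leave the first-listed table and join autoimmune and traumatic cases, and the between-arm contrast in that first table narrows. Arterial thromboembolic events, another Table 2 risk, are handled differently: SAP 8.2 gives them one table with a stated case definition.

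**Working it through.** The documents give no IOI rate or count, so there is no figure of the plan's own to reproduce. The check has two parts.

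**1. Can any planned frequency table give the number of participants with any IOI?**

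- *Three IOI tables.* Each is a subset by cause. A participant with episodes of different cause is counted in two of them.
- *Ocular TEAE/TESAE table and its severity version.* They contain every treatment-emergent ocular IOI. The levels named for once-per-participant counting are any event, system organ class and preferred term. IOI is spread over several terms, the rows cannot be summed to participants, and no IOI group level is named.
- *Related and procedure-related tables.* They cover all related ocular events and are not specific to IOI.
- *AESI table.* Protocol 8.3.6 names only severe IOI as a criterion, and the SAP combines study-eye, fellow-eye and non-ocular events in this table.
- *Listings.* They hold every event, but give no incidence by arm.

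None gives the figure. If the three IOI tables show a, b and c participants, the number with any IOI lies between max(a, b, c) and a + b + c. With assumed counts 3, 1 and 2 in an arm of 120 (about 120 per arm, SAP 9.0):

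- lower bound: max(3, 1, 2) = 3, and 3/120 = 2.5%
- upper bound: 3 + 1 + 2 = 6, and 6/120 = 5.0%

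**2. How far could the first-listed table fall below the any-cause rate?**

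Let T be the participants with IOI and m those moved out as drug toxicity. For simplicity, assume no infectious, autoimmune or traumatic cases and one episode per participant. The first table then shows (T − m)/120 against T/120. T and m are assumptions.

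| T | Any-cause rate | m | First-listed table |
|---|---|---|---|
| 6 | 6/120 = 5.0% | 0 | 6/120 = 5.0% |
| 6 | 5.0% | 3 | 3/120 = 2.5% |
| 8 | 8/120 = 6.7% | 2 | 6/120 = 5.0% |
| 8 | 6.7% | 4 | 4/120 = 3.3% |
| 8 | 6.7% | 6 | 2/120 = 1.7% |

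For T = 6 the exact (Clopper-Pearson) 95% interval is 1.9% to 10.6%, and Fisher's exact test against 0/120 gives p = 0.029. With 3 moved, the first table's interval is 0.5% to 7.1% and p = 0.25. The SAP plans no such test. The p-values only show how the apparent contrast changes. With m = 0 there is no gap.

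**The case against.** The strongest reply is that nothing is hidden. The three categories together cover every cause, every treatment-emergent ocular IOI is also in the overall ocular table, severe IOI is an AESI, and all events are listed by treatment group and subject. An IOI judged related to KSI-301 gains a place in the related-event table, and SAP 8.2 counts missing relatedness as related. Overlap needs one participant with episodes of different cause, which the listings would settle when cases are few. No hypothesis test or alpha depends on these tables.

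Most of this stands, and it rules out two stronger readings that a reader might infer. The first is that the SAP takes drug-caused inflammation out of its main IOI table and so understates the risk. The SAP names no main table, drops no event, and does not say that drug toxicity means KSI-301. Understatement follows only if the first-listed table is read as the IOI rate and events have been classed that way. The second is that the sponsor would assign causes after unmasking. The documents are silent on who assigns them. They have the masked Investigator assess causality (protocol synopsis), keep the sponsor masked (protocol 6.3.2), and leave unmasking to a separate document (SAP 1.0 and 4.3.1).

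The reply does not supply the missing rate. A reader should not have to rebuild a core safety incidence from listings, and the related-event table does not isolate IOI.

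**Conclusion.** The point holds as a gap in the planned tabulation. SAP 8.2 divides a named KSI-301 risk by cause, pools drug-toxicity cases with autoimmune and traumatic ones, and gives no once-per-participant incidence of any IOI by arm. The planned frequency tables cannot supply it.

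That conclusion rests on the table lists alone. Any shortfall in the first-listed table further requires that drug toxicity includes KSI-301 and that events are classed that way. Its size is unknown: in the assumed examples it runs from nothing to 5 percentage points (6.7% against 1.7%). Those figures illustrate the mechanism and predict nothing about this trial. The undefined category and the unstated rule for assigning cause are missing details, secondary to the missing total.

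**What to change.** In SAP 8.2, add a table of any study-eye IOI TEAE/TESAE, all causes, by arm and maximum severity, counting each participant once from a prespecified list of preferred terms. Beneath it:

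- show infectious and non-infectious IOI;
- inside non-infectious, give IOI related to study drug or procedure its own row, not pooled with autoimmune or traumatic cases.

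If the split by cause is kept, present it as a breakdown of that total, define drug toxicity, state who assigns the cause, and require assignment before the Week 48 unmasking. SAP 7.1.1.4 already sets that timing for intercurrent events.

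The cost is SAP wording and one more table from adverse event data already collected, with no change to trial procedures. The IOI figure that readers quote may be higher than the one in the first-listed table.
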